# Appendix A

| Pregnancy              |                                                                                           |
|------------------------|-------------------------------------------------------------------------------------------|
| Dx codes        |                                                                                           |
| 650                    | NORMAL DELIVERY                                                                           |
| 660                    | OBSTRUCTED LABOR                                                                          |
| 661                    | ABNORMALITY OF FORCES OF LABOR                                                            |
| 662                    | LONG LABOR                                                                                |
| 663                    | UMBILICAL CORD COMPLICATIONS DURING LABOR AND DELIVERY                                    |
| 664                    | TRAUMA TO PERINEUM AND VULVA DURING DELIVERY                                              |
| 665                    | OTHER OBSTETRICAL TRAUMA                                                                  |
| 667                    | RETAINED PLACENTA OR MEMBRANES WITHOUT HEMORRHAGE                                         |
| 668                    | COMPLICATIONS OF THE ADMINISTRATION OF ANESTHETIC OR OTHER SEDATION IN LABOR AND DELIVERY |
| 669.94                 | UNSPECIFIED COMPLICATION OF LABOR AND DELIVERY POSTPARTUM CONDITION OR COMPLICATION       |
| V24                    | POSTPARTUM CARE AND EXAMINATION                                                           |
| V24.0                  | POSTPARTUM CARE AND EXAMINATION IMMEDIATELY AFTER DELIVERY                                |
| V24.1                  | POSTPARTUM CARE AND EXAMINATION OF LACTATING MOTHER                                       |
| V24.2                  | ROUTINE POSTPARTUM FOLLOW                                                                 |
| V27                    | OUTCOME OF DELIVERY                                                                       |
| V27.0                  | MOTHER WITH SINGLE LIVEBORN                                                               |
| V27.1                  | MOTHER WITH SINGLE STILLBORN                                                              |
| V27.2                  | MOTHER WITH TWINS BOTH LIVEBORN                                                           |
| V27.3                  | MOTHER WITH TWINS ONE LIVEBORN AND ONE STILLBORN                                          |
| V27.4                  | MOTHER WITH TWINS BOTH STILLBORN                                                          |
| V27.5                  | MOTHER WITH OTHER MULTIPLE BIRTH ALL LIVEBORN                                             |
| V27.6                  | MOTHER WITH OTHER MULTIPLE BIRTH SOME LIVEBORN                                            |
| V27.7                  | MOTHER WITH OTHER MULTIPLE BIRTH ALL STILLBORN                                            |
| V27.9                  | MOTHER WITH UNSPECIFIED OUTCOME OF DELIVERY                                               |
| Procedure codes |                                                                                           |
| 72.0                   | LOW FORCEPS OPERATION                                                                     |
| 72.1                   | LOW FORCEPS OPERATION WITH EPISIOTOMY                                                     |
| 72.2                   | MID FORCEPS OPERATION                                                                     |
| 72.21                  | MID FORCEPS OPERATION WITH EPISIOTOMY                                                     |
| 72.29                  | OTHER MID FORCEPS OPERATION                                                               |
| 72.3                   | HIGH FORCEPS OPERATION                                                                    |
| 72.31                  | HIGH FORCEPS OPERATION WITH EPISIOTOMY                                                    |
| 72.39                  | OTHER HIGH FORCEPS OPERATION                                                              |

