| Women of childbearing potential (WOCBP) must be using an adequate method of contraception to avoid pregnancy throughout the study in such a manner that the risk of pregnancy is minimized. (Additional details in Supplementary Appendix )                                                                                                                                                                                                                                          | N/A                                                                                                                                                                                                                                                         | Criteria captured as an exclusion criteria in the Pregnancy measure                                                                                                                                                                                                              |                                                                                                                                                                                                                                                                                                                                                                                                                                                                                                                    |

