| WOCBP who are unwilling or unable to use an acceptable method of birth control (such as oral contraceptives, other hormonal contraceptives [vaginal products, skin patches, or implanted or injectable products], or mechanical products such as an intrauterine device or barrier methods [diaphragm, condoms, spermicides]) to avoid pregnancy for the entire study.                                                                                                                               | Measured 180 days prior to and including day of drug initiation in any diagnosis position and in an inpatient or outpatient care setting

See 'Pregnancy' sheet for codes                                                                             |                                                                                                                                                                                                                                                                                  |                                                                                                                                                                                                                                                                                                                                                                                                                                                                                                                    |

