| Women who are pregnant or breastfeeding.                                                                                                                                                                                                                                                                                                                                                                                                                                                             |                                                                                                                                                                                                                                                             |                                                                                                                                                                                                                                                                                  |                                                                                                                                                                                                                                                                                                                                                                                                                                                                                                                    |

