| Women with a positive pregnancy test on enrollment or prior to investigational product administration.                                                                                                                                                                                                                                                                                                                                                                                               |                                                                                                                                                                                                                                                             |                                                                                                                                                                                                                                                                                  |                                                                                                                                                                                                                                                                                                                                                                                                                                                                                                                    |

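### The printed Pregnancy code sheet has no code for an ongoing pregnancy, so a woman pregnant at drug start with no labour, delivery or other listed code by that day stays in the cohort

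*Combined protocol and SAP*

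**What the plan says.** Section 5.2.2 says the eligibility criteria follow the trial as closely as possible and sends the reader to Appendix A for definitions.

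Appendix A lists these trial exclusions: "Women who are pregnant or breastfeeding", and "Women with a positive pregnancy test on enrollment or prior to investigational product administration". They share a block with the contraception exclusion, whose implementation cell reads "Measured 180 days prior to and including day of drug initiation in any diagnosis position and in an inpatient or outpatient care setting" and then "See 'Pregnancy' sheet for codes". On the inclusion side, the contraception row is marked N/A with the comment "Criteria captured as an exclusion criteria in the Pregnancy measure". The negative-test row has no entry of its own; the table may have merged cells there.

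The Pregnancy sheet, also in Appendix A, opens with "NORMAL DELIVERY" (650). It goes on through labour and delivery complications, postpartum care including "POSTPARTUM CARE AND EXAMINATION IMMEDIATELY AFTER DELIVERY" (V24.0) and "POSTPARTUM CARE AND EXAMINATION OF LACTATING MOTHER" (V24.1), the outcome-of-delivery codes (V27.x), and procedures in 72.x to 75.x. It prints no ICD-10 codes. The note at the top of Appendix A says full ICD-10 lists are in an external folder and were produced by mapping from ICD-9.

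The flowchart in Section 5.3 shows Exclusion #1 (pregnancy) removing 14 patients in Optum, 42 in MarketScan and 22 in Medicare.

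**The concern.** The trial criterion describes a woman's state when she starts drug: pregnant, or breastfeeding. The printed codes describe events that finish a pregnancy or follow one. Searched backward from drug start, they mostly find women who are no longer pregnant. A woman in mid-pregnancy would normally have none of them yet, so she passes the exclusion.

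What is at stake is fidelity to the trial. Appendix A marks many criteria it cannot measure as N/A. Here it says the measure captures the criterion, and the flowchart row is labelled pregnancy. A reader would conclude that pregnant women were removed. Nothing later makes up for the gap: Appendix B lists no pregnancy covariate, so women who pass the exclusion are not matched on pregnancy either.

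**Working it through.** **1. The plan's own figures (Section 5.3).** Patients before the row, minus those removed:

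- Optum: 8,593 − 14 = 8,579, as printed; 14/8,593 = 0.16%.
- MarketScan: 8,382 − 42 = 8,340, as printed; 42/8,382 = 0.50%.
- Medicare: 20,793 − 22 = 20,771, as printed; 22/20,793 = 0.11%.
- Together: 14 + 42 + 22 = 78 of 8,593 + 8,382 + 20,793 = 37,768, or 0.21%.

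**2. The code sheet, read label by label.**

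- Diagnosis codes: 650, 660 to 665, 667, 668 and 669.94 (10); V24 and V24.0 to V24.2 (4); V27, V27.0 to V27.7 and V27.9 (10). Total 24.
- Procedure codes: 20 in 72.x, 20 in 73.x, 8 in 74.x and 5 in 75.x. Total 53.
- 24 + 53 = 77. Of these, 75 belong to the labour, delivery and postpartum groups. Two of the 75 (665 and 75.9) have general obstetric labels. The other two codes are 74.3 (ectopic removal) and 74.91 (termination by hysterotomy), and each ends a pregnancy.
- Labels denoting prenatal supervision, a positive test, gestational age or an antenatal condition: none.

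**3. Criterion against rule.**

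| Woman at drug start | Trial criteria as listed | Printed rule |
|---|---|---|
| Pregnant, no listed code from day −180 to day 0 | Excluded | Kept |
| In labour or delivering on day 0 | Excluded | Excluded, since day 0 is in the window |
| Delivered in the last 180 days, breastfeeding | Excluded | Excluded if coded |
| Delivered in the last 180 days, not breastfeeding | Not excluded by this criterion; other criteria may apply | Excluded if coded |

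The first row is the gap.

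**4. Possible size.** The documents give neither the number pregnant at drug start nor an age-by-sex table, so this is an illustration only. Assume age and sex are independent within each matched database (Appendix B). Women aged 18 to 54 are then approximately (patients aged 18 to 54) × (females) / (patients):

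- Optum: 385 × 511 / 980 = 200.8.
- MarketScan: 1,474 × 1,326 / 2,762 = 707.7.
- Medicare: 902 × 1,831 / 3,398 = 486.0.
- Sum: about 1,394.

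If 0% to 5% of them were pregnant (an assumed range), 0 to about 70 patients would be removed, at most 70/7,140 = 1.0%.

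**5. Power.** Section 10 gives D = 7,140 × 13.74/1,000 = 98.10 expected events, margin 1.8 and hazard ratio 0.84. Φ(√(D/4) × ln(1.8/0.84) − 1.96) = 0.9652, which reproduces the stated 0.965194. At the 5% end, suppose each removed woman also loses her matched partner: D = (7,140 − 139.4) × 13.74/1,000 = 96.2 and power is 0.962.

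**The case against.** Four objections deserve an answer.

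**The ICD-10 list cannot be seen.** Cohort entry runs to the end of 2017, the end of 2018 and March 2020 in the three databases, and the mapped list is outside the document. This stands. Because the list is described as mapped from ICD-9, the same gap is likely, but it is an inference. A reader might also infer that all 78 exclusions came through end-of-pregnancy codes; the documents do not show which codes removed them.

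**Part of the sheet is on target.** The criterion also covers breastfeeding, V24.1 names a lactating mother, and delivery and postpartum codes are a reasonable proxy. This stands too: one limb is partly served, so it would be wrong to say that the sheet implements nothing in the criterion.

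**Removing recently delivered women may do no harm.** A reader might infer that the rule drops women whom the trial excluded only if they were breastfeeding. The documents do not support that. Other listed trial criteria could also have removed such women: a provoked index event without a persistent risk factor (set to N/A here) and major surgery within two months. The emulation picks major surgery from 35.x to 84.x, a range that contains the delivery procedures, and does not show which were picked.

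**No consequence is shown.** The number of pregnant women is unknown, and nothing shows that they would fall unevenly between apixaban and warfarin. This limits the weight of the point. It does not close the gap between the criterion and its code list.

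**Conclusion.** The point holds for the printed sheet, with a small expected effect. None of its 77 codes marks an ongoing pregnancy, so the backward search to day 0 keeps a woman who is pregnant at drug start and has no listed event by then. The trial excluded her, and Appendix A says the Pregnancy measure deals with the matter.

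The conclusion rests on the printed labels. It assumes that the sheet is the ICD-9 list actually run and, for ICD-10, that the mapping added no ongoing-pregnancy codes.

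It is tempting to go further and call the hazard ratio biased. The documents do not support that: they give no count of pregnant women, no split by arm and no outcome risk for them. Under the assumed 0% to 5% range, at most about 1.0% of the matched cohort is involved and power barely moves. This is a fault in fidelity and labelling, cheap to correct, and not a threat to the main result as far as the documents show.

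**What to change.** Add ICD-9 and ICD-10 codes for ongoing pregnancy to the Pregnancy sheet: prenatal supervision, antenatal conditions and prenatal procedures. Count such a code when no later end-of-pregnancy code comes before the index date. Keep the delivery and postpartum codes as the breastfeeding proxy, and say that this is their purpose. Check the ICD-10 list in the external folder at the same time. If it already holds ongoing-pregnancy codes, say so in Appendix A.

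Then rerun the pregnancy row of the flowchart and every later step: the remaining exclusions, the propensity-score match, Appendix B, and the counts and power in Sections 9 and 10. If the team prefers not to change the list, the minimum is to state that current pregnancy is not captured and to correct the comment on the contraception row.

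The cost is one code-list edit and one rerun, with a few patients moving in or out of the match. In this document the date for the comparative analyses in Section 13 is still blank, so on its face the change can be made before treatment groups are compared on outcome.

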## Appendix A

- 72.4 FORCEPS ROTATION OF FETAL HEAD
- 72.5 BREECH EXTRACTION
- 72.51 PARTIAL BREECH EXTRACTION WITH FORCEPS TO AFTERCOMING HEAD
- 72.52 OTHER PARTIAL BREECH EXTRACTION
- 72.53 TOTAL BREECH EXTRACTION WITH FORCEPS TO AFTERCOMING HEAD
- 72.54 OTHER TOTAL BREECH EXTRACTION
- 72.6 FORCEPS APPLICATION TO AFTERCOMING HEAD
- 72.7 VACUUM EXTRACTION
- 72.71 VACUUM EXTRACTION WITH EPISIOTOMY
- 72.79 OTHER VACUUM EXTRACTION
- 72.8 OTHER SPECIFIED INSTRUMENTAL DELIVERY
- 72.9 UNSPECIFIED INSTRUMENTAL DELIVERY
- 73.0 ARTIFICIAL RUPTURE OF MEMBRANES
- 73.01 INDUCTION OF LABOR BY ARTIFICIAL RUPTURE OF MEMBRANES
- 73.09 OTHER ARTIFICIAL RUPTURE OF MEMBRANES
- 73.1 OTHER SURGICAL INDUCTION OF LABOR
- 73.2 INTERNAL AND COMBINED VERSION AND EXTRACTION
- 73.21 INTERNAL AND COMBINED VERSION WITHOUT EXTRACTION
- 73.22 INTERNAL AND COMBINED VERSION WITH EXTRACTION
- 73.3 FAILED FORCEPS
- 73.4 MEDICAL INDUCTION OF LABOR
- 73.5 MANUALLY ASSISTED DELIVERY
- 73.51 MANUAL ROTATION OF FETAL HEAD
- 73.59 OTHER MANUALLY ASSISTED DELIVERY
- 73.6 EPISIOTOMY
- 73.8 OPERATIONS ON FETUS TO FACILITATE DELIVERY
- 73.9 OTHER OPERATIONS ASSISTING DELIVERY
- 73.91 EXTERNAL VERSION ASSISTING DELIVERY
- 73.92 REPLACEMENT OF PROLAPSED UMBILICAL CORD
- 73.93 INCISION OF CERVIX TO ASSIST DELIVERY
- 73.94 PUBIOTOMY TO ASSIST DELIVERY
- 73.99 OTHER OPERATIONS ASSISTING DELIVERY
- 74.0 CLASSICAL CESAREAN SECTION
- 74.1 LOW CERVICAL CESAREAN SECTION
- 74.2 EXTRAPERITONEAL CESAREAN SECTION

## Appendix A

- 74.3 REMOVAL OF EXTRATUBAL ECTOPIC PREGNANCY
- 74.4 CESAREAN SECTION OF OTHER SPECIFIED TYPE
- 74.9 CESAREAN SECTION OF UNSPECIFIED TYPE
- 74.91 HYSTEROTOMY TO TERMINATE PREGNANCY
- 74.99 OTHER CESAREAN SECTION OF UNSPECIFIED TYPE
- 75.4 MANUAL REMOVAL OF RETAINED PLACENTA
- 75.5 REPAIR OF CURRENT OBSTETRIC LACERATION OF UTERUS
- 75.6 REPAIR OF OTHER CURRENT OBSTETRIC LACERATION
- 75.7 MANUAL EXPLORATION OF UTERINE CAVITY, POSTPARTUM
- 75.9 OTHER OBSTETRIC OPERATIONS

# Appendix A

|                                            |                                                                                       |
|--------------------------------------------|---------------------------------------------------------------------------------------|
| Title                               |                                                                                       |
| Venous Thromboembolism (VTE)               |                                                                                       |
| ICD-9 Dx inpatient primary position |                                                                                       |
| PE                                  |                                                                                       |
| 415.1                                      | PULMONARY EMBOLISM AND INFARCTION                                                     |
| 415.11                                     | IATROGENIC PULMONARY EMBOLISM AND INFARCTION                                          |
| 415.19                                     | OTHER PULMONARY EMBOLISM AND INFARCTION                                               |
| DVT                                 |                                                                                       |
| 451.1                                      | PHLEBITIS AND THROMBOPHLEBITIS OF DEEP VEINS OF LOWER EXTREMITIES                     |
| 451.11                                     | PHLEBITIS AND THROMBOPHLEBITIS OF FEMORAL VEIN (DEEP) (SUPERFICIAL)                   |
| 451.19                                     | PHLEBITIS AND THROMBOPHLEBITIS OF OTHER                                               |
| 451.2                                      | PHLEBITIS AND THROMBOPHLEBITIS OF LOWER EXTREMITIES UNSPECIFIED                       |
| 451.81                                     | PHLEBITIS AND THROMBOPHLEBITIS OF ILIAC VEIN                                          |
| 451.9                                      | PHLEBITIS AND THROMBOPHLEBITIS OF UNSPECIFIED SITE                                    |
| 453                                        | BUDD-CHIARI SYNDROME                                                                  |
| 453.1                                      | THROMBOPHLEBITIS MIGRANS                                                              |
| 453.2                                      | EMBOLISM AND THROMBOSIS OF INFERIOR VENA CAVA                                         |
| 453.4                                      | ACUTE VENOUS EMBOLISM AND THROMBOSIS OF DEEP VESSELS OF LOWER EXTREMITY               |
| 453.4                                      | ACUTE VENOUS EMBOLISM AND THROMBOSIS OF UNSPECIFIED DEEP VESSELS OF LOWER EXTREMITY   |
| 453.41                                     | ACUTE VENOUS EMBOLISM AND THROMBOSIS OF DEEP VESSELS OF PROXIMAL LOWER EXTREMITY      |
| 453.42                                     | ACUTE VENOUS EMBOLISM AND THROMBOSIS OF DEEP VESSELS OF DISTAL LOWER EXTREMITY        |
| 453.5                                      | CHRONIC VENOUS EMBOLISM AND THROMBOSIS OF DEEP VESSELS OF LOWER EXTREMITY             |
| 453.5                                      | CHRONIC VENOUS EMBOLISM AND THROMBOSIS OF UNSPECIFIED DEEP VESSELS OF LOWER EXTREMITY |
| 453.51                                     | CHRONIC VENOUS EMBOLISM AND THROMBOSIS OF DEEP VESSELS OF PROXIMAL LOWER EXTREMITY    |
| 453.52                                     | CHRONIC VENOUS EMBOLISM AND THROMBOSIS OF DEEP VESSELS OF DISTAL LOWER EXTREMITY      |
| 453.8                                      | ACUTE VENOUS EMBOLISM AND THROMBOSIS OF OTHER SPECIFIED VEINS                         |
| 453.82                                     | ACUTE VENOUS EMBOLISM AND THROMBOSIS OF DEEP VEINS OF UPPER EXTREMITY                 |
| 453.83                                     | ACUTE VENOUS EMBOLISM AND THROMBOSIS OF UPPER EXTREMITY UNSPECIFIED                   |
| 453.84                                     | ACUTE VENOUS EMBOLISM AND THROMBOSIS OF AXILLARY VEINS                                |
| 453.85                                     | ACUTE VENOUS EMBOLISM AND THROMBOSIS OF SUBCLAVIAN VEINS                              |
| 453.86                                     | ACUTE VENOUS EMBOLISM AND THROMBOSIS OF INTERNAL JUGULAR VEINS                        |
| 453.87                                     | ACUTE VENOUS EMBOLISM AND THROMBOSIS OF OTHER THORACIC VEINS                          |
| 453.89                                     | ACUTE VENOUS EMBOLISM AND THROMBOSIS OF OTHER SPECIFIED VEINS                         |

